3.2.4 Patient Baseline data, Medical history and Disposition

Summary tables in this section will be presented for the FAS by the group presented in [Section 3.2.1](#).

Baseline data (demographic, disease history and baseline disease characteristics) will be summarized. It will also be displayed in the patient data listings.

- Demographic including age, gender, ethnicity, race, weight and BMI will be summarized using descriptive statistics by the group presented in [Section 3.2.1](#). Age is calculated by using the informed consent date of the open-label study and birth date. Gender, ethnicity and race for Group 1 and 2 patients were collected in each index study.
- Disease history includes duration of FCS diagnosis at screening, age at FCS diagnosis, lipemia retinalis, eruptive xanthomas history, pancreatitis history, glybera treatment history, confirmation for known loss-of-function mutations in Type 1-causing genes, documentation of post heparin plasma LPL activity <=20% of normal based on medical history, confirmation for type 1 phenotype based on genetic sequencing results, post heparin plasma LPL activity <=20% of normal based on lab results, , and history of type II diabetes.

- Baseline disease characteristics includes: body weight, height at Day 1 of the Open-label study, Body Mass Index (BMI) , fasting lipids results including TG, LDL-C, HDL-C, Total Cholesterol, non-HDL-C, VLDL-C, apoA-1, apoB and apoC-III.

Medical history collected in the open-label study will be coded by Medical Dictionary for Regulatory Activities (MedDRATM) dictionary version 19.1 and will be summarized by system organ class and preferred term for the Safety Set. Medical history will also be provided in the patient data listings.

Patient disposition of the open-label study will be summarized for all enrolled patients. The number of patients enrolled, dosed, completed treatment, along with reasons for discontinuing treatment and withdrawing from the study, completed post-treatment follow-up, along with reasons for early terminating post-treatment follow-up, will be presented. Patient disposition through CS6 and CS7 will also be summarized.

Treatment discontinuation by month will be presented through index studies and open-label study to present number of patients discontinued in each study month and corresponding discontinuation reason, and remaining number of patients in the study.

Summary of discontinuation rate per patient year of exposure in the index studies and open-label study overall will be generated.

Kaplan Meier Plot of Treatment Continuation will be provided for below comparisons:

- CS6 volanesorsen arm vs CS7 treatment naive group in patients with history of pancreatitis
- CS6 volanesorsen arm vs CS7 treatment naive group in patients with history of pancreatitis through Month 12
- CS6 volanesorsen arm vs CS7 treatment naive group in safety set through Month 12

Listing of patient disposition will also be provided.

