3 ANALYSIS PLAN

3.1 Statistical Design Summary

This is a multi-center open-label study of:

Group 1: ISIS 304801-CS6 (index study) roll over FCS patients

Group 2: ISIS 304801-CS16 (index study) roll over FCS patients

Group 3: FCS patients who did not participate in the ISIS 304801-CS6 or ISIS 304801-CS16 index studies.

Group 1 and Group 2 patients who complete one of the index studies and who are qualified plus Group 3 patients who are screened and qualified will be enrolled to this open-label study. The safety and efficacy of extended dosing with volanesorsen in patients with FCS will be evaluated by summary tables rather than hypothesis tests. Missing data will not be imputed.

3.1.2 *Sample Size Consideration*

No sample size calculations were performed as this is an open-label extension study.

3.1.3 *Planned Interim Analysis*

An interim analysis may be conducted after the last patient's Week 13 visit of the open-label study or after the database of the ISIS 304801-CS6 and ISIS 304801-CS16 index studies are locked and unblinded.

Planned summaries and patient data listings for disposition, demographic, efficacy and safety will be included in this interim analysis.

Additional interim analyses will be performed to support regulatory filing activities.

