	104	722	674 to 743
	117	813	744 to 858
	130 (France)	904	859 to 949
Abdominal Pain			
	m	$n \times 7 + 1$	$mx7+3 \text{ to } mx7-3,$ $m = -1, -2, \dots$
	...		
	-2	-13	-11 to -17
	-1	-6	-4 to -10
	1	1	1 to -3
	2	8	5 to 11

	3	15	12 to 18
	n	(n-1) × 7+1	(n-1) × 7-2 to (n-1) × 7+4
	...		
MRI			
	Screening	NA	≤ 14
	52	358	298 to 418
Quality of Life Assessments (EQ-5D, SF-36)			
	1	1	1
	13	85	55 to 115
	26	176	146 to 206
	52	358	328 to 404
	65	449	405 to 479
	78 (France)	540	496 to 570
	117 (France)	813	769 to 843
	130 (France)	904	860 to 934

Note: Regarding lipid measurements for efficacy analyses, mapped observed assessments defined in this table will be derived further. The derivations for baselines are described in [section 3.2.3](#). The derivations for Month 3, 6 and 12 are described in [section 3.3.1](#).

Non-efficacy by visit assessments will be summarized using the visit labels provided in the data. Multiple results with the same visit label will be averaged.

Unscheduled results and data from local labs will not be included in the by visit summaries but will be used in the determination of baseline, in the laboratory abnormality, stopping rule, and platelets reduction analyses presented in data listings.

Unscheduled results from the central lab will be used in the determination of baseline, laboratory abnormality summaries, and shift from **safety baseline** to worst post-baseline, and platelets reduction analyses only, and presented in data listings. Local lab data will be only used in platelet analyses (including by visit summaries, abnormality summary, shift from Baseline to worst post-baseline, reduction analyses), and presented in data listings.

Summary tables and figures will NOT be presented by the treatment group in each index study (ISIS 304801-CS6 or ISIS 304801-CS16) and the newly enrolled patients as a separate group per protocol. Per Sponsor decision, most summary tables and figures will be presented in the following groups, i.e. Treatment naive group, CS6-Volanesorsen, CS16-Volanesorsen, and Overall, if applicable.

Note: “Treatment naive group” for most tables and figures is a combined group of subjects including CS7-New, CS6-Placebo and CS16-Placebo. When the summary is based on **Index Study Baseline**, “Treatment naive group” is a combined group of subjects including CS6-Placebo and CS16-Placebo.

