3.2.2 Patient Population Analyzed

The following analysis populations will be used for the analysis of data as described within each analysis set.

Full Analysis Set (FAS): All patients who are enrolled and received at least one dose of Study Drug and who have an open-label study baseline TG assessment. The FAS represents the practically-feasible intent-to-treat (ITT) population as delineated in ICH Guideline E9.

The significant deviation criteria are listed in Appendix A.

All protocol deviations will be listed in the patient data listings.

Safety Set: All patients who are enrolled and receive at least one dose of Study Drug. Group 1 and Group 2 patients will be summarized in the actual treatment group patients received during index study. Patients randomized to receive placebo in the index study, incorrectly treated with volanesorsen during the index study treatment period will be counted in the volanesorsen group from the first dose of volanesorsen received.

PK Population: All patients who are enrolled and receive at least one dose of Study Drug, and have at least one post first dose PK sample collected, analyzed, and not excluded by PK scientist as the PK result was considered to be an outlier. Group 1 and Group 2 patients will be summarized in the actual treatment group patients received during index study. Patients randomized to receive placebo in the index study, incorrectly treated with volanesorsen during the index study treatment period will be counted in the volanesorsen group from the first dose of volanesorsen received. Group 3 patients will be summarized under Treatment naive group.

All efficacy endpoints will be assessed in the FAS. All safety assessments will be performed on the Safety Set. PK endpoints will be assessed in the PK Set as applicable.

Analysis populations will be summarized with counts and percentages by the group presented in [Section 3.2.1](#).

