For patients in the PK subgroup only, non-compartmental PK analysis of volanesorsen will be carried out on each individual patient data set using data collected in the open-label study from the intensive PK subgroup, following a single dose (i.e., single-dose PK) or multiple doses (i.e., steady-state PK), depending on their earlier treatment in the index studies (Group 1 and Group 2 Patient). On Week 1 Day 1 of the open-label study, patients who received placebo in the index study (and all patients in Group3) will receive the first treatment of volanesorsen (single-dose PK), while patients who received volanesorsen in the index studies had been on volanesorsen treatment for 12 months (ISIS 304801-CS6) or 6 months (ISIS 304801-CS16), thus the PK data collected from these patients reflect steady-state PK. The maximum observed drug concentration (C_{\max}) and the time taken to reach C_{\max} (T_{\max}) will be obtained directly from the concentration-time data. Area under the plasma concentration-time curve from time zero to 24 hours (AUC_{0-24h}) will be calculated using the linear trapezoidal rule. Apparent systemic (plasma) clearance after SC administration (CL_{0-24h}/F) will be calculated from $CL_{0-24h}/F = \text{Actual Dose}/AUC_{0-24h}$. Mean residence time (MRT) from time zero to 24 hours after the SC administration will be calculated from the equation, $MRT_{0-24h} = AUMC_{0-24h}/AUC_{0-24h}$, where $AUMC_{0-24h}$ is the area under the moment plasma concentration-time curve from time zero to 24 hours after the SC administration. Other PK parameters, as appropriate, may be determined or calculated at the discretion of the PK scientist.

Plasma PK parameters will be summarized using descriptive statistics for 2 groups (Treatment naive group and CS6-Volanesorsen and CS16-Volanesorsen Combined), with and without stratification by IM status.

Population PK, PK/PD, and covariate analysis may be performed if deemed appropriate, and results will be reported separately. This SAP do not include relevant analysis plan.

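### Section 3.2.4 leaves open which patients feed the index-period discontinuation outputs, and the analysis sets it names, taken literally, would leave index volanesorsen time almost free of discontinuations

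*SAP*

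**What the plan says.** Section 3.1 sets the entry condition for rollovers: "Group 1 and Group 2 patients who complete one of the index studies and who are qualified" are enrolled, together with screened and qualified Group 3 patients. Section 3.4.1.2 describes those who took active drug in the index studies as patients who "had been on volanesorsen treatment for 12 months (ISIS 304801-CS6) or 6 months (ISIS 304801-CS16").

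Section 3.2.2 defines one Safety Set, "Safety Set: All patients who are enrolled and receive at least one dose of Study Drug", and a FAS that also needs an open-label baseline triglyceride value. No CS6 or CS16 analysis set is defined.

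Section 3.2.4 opens with a default: "Summary tables in this section will be presented for the FAS by the group presented in" section 3.2.1. It then plans:
- discontinuations with reasons by study month, through the index studies and CS7;
- a rate, "Summary of discontinuation rate per patient year of exposure in the index studies and open-label study overall will be generated";
- three Kaplan-Meier comparisons of the CS6 volanesorsen arm with the CS7 treatment naive group. Two are in patients with a history of pancreatitis and name no analysis set. The third is "CS6 volanesorsen arm vs CS7 treatment naive group in safety set through Month 12".

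Under section 3.2.1 the treatment naive group, for most outputs, "is a combined group of subjects including CS7-New, CS6-Placebo and CS16-Placebo". Section 3.2.4 gives no time origin, event definition or censoring rule for the plots.

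**The concern.** A patient who stopped volanesorsen during CS6 or CS16 and did not complete the index study is not in CS7, and so not in the FAS or Safety Set as defined. If those sets supply the patients while the clock starts at the first index dose, the index months add time at risk but almost no events. The CS6 curve is then high because of the entry rule, and the combined rate is diluted. The treatment naive group gets no such protected period, because its volanesorsen time starts at CS7 Day 1. A difference between the curves, or a low overall rate, could be taken as evidence about how well volanesorsen is tolerated over time when it partly reflects who was allowed to roll over.

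**Working it through.** **No plan figure to reproduce.** The SAP states no discontinuation rate, event count, sample size calculation or power. The arithmetic below shows only the size of the effect under the literal reading.

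**Inputs**
- Event-free index time t0: 1.0 year for CS6 and 0.5 year for CS16 (section 3.4.1.2). This takes completing the index study to mean completing treatment, as that section describes.
- Open-label treatment time t1: 1 year, or 2 years with the optional further 52 weeks (section 1.1).
- Annual discontinuation probability p on volanesorsen: 10% to 40%. This is an assumption.

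**Formulas** (constant hazard, time at risk ending at discontinuation)
- Hazard: h = -ln(1 - p). This is the rate if all index-treated patients are counted.
- Open-label events per rollover: E = 1 - exp(-h × t1).
- Open-label time per rollover: E / h.
- Rollovers-only combined rate: E / (t0 + E / h).

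**Worked case** (p = 20%, CS6, t1 = 1 year)
- h = -ln(0.8) = 0.223
- E = 0.200
- Open-label time = 0.200 / 0.223 = 0.896 years
- Combined rate = 0.200 / (1 + 0.896) = 0.105 per patient-year
- Ratio to h = 0.47

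**Results: combined rate per patient-year (ratio to h)**

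| p | h | CS6, 1 y | CS6, 2 y | CS16, 1 y | CS16, 2 y |
|---|---|---|---|---|---|
| 10% | 0.105 | 0.051 (0.49) | 0.068 (0.64) | 0.069 (0.65) | 0.082 (0.78) |
| 20% | 0.223 | 0.105 (0.47) | 0.138 (0.62) | 0.143 (0.64) | 0.170 (0.76) |
| 30% | 0.357 | 0.163 (0.46) | 0.210 (0.59) | 0.224 (0.63) | 0.264 (0.74) |
| 40% | 0.511 | 0.224 (0.44) | 0.284 (0.56) | 0.312 (0.61) | 0.365 (0.71) |

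**Kaplan-Meier at Month 12 from first index dose.** Rollovers only: about 100% whatever p is. Whole CS6 arm: 1 - p, that is 90% down to 60%.

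**Full-arm reading.** If everyone dosed with volanesorsen in the index studies is counted, the combined rate equals h and the ratio is 1.0.

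**Limit of the illustration.** Section 3.2.1 runs patient-years from an unspecified treatment start date to the latest visit or data cutoff, not to discontinuation. The table therefore shows the mechanism and does not predict the rate the SAP's own formula would return.

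**The case against.** A reader might infer that these outputs do rest on rollovers, so that index time is event-free by design. The SAP does not support that as settled. Section 3.2.4 speaks of the CS6 volanesorsen arm, not the CS7 display label CS6-Volanesorsen. Where the SAP means rollovers it says so: section 3.3.5 refers to CS6 subjects who roll over to CS7, and section 3.2.4 does not use that qualifier. Discontinuations with reasons in each index month, and disposition through CS6 and CS7, make sense only if index dropouts are counted. A curve fixed near 100% to Month 12 would be pointless. The FAS default covers summary tables, not plots, and the section itself departs from it for medical history and disposition. All of this stands, and it makes the full-arm intent plausible.

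A reader might also infer that the comparison is biased in the same way on either reading. It is not. With the full arm there is no event-free time. What remains is that CS6-Placebo and CS16-Placebo members of the naive group had already completed an index study, while CS7-New patients had not. That selection is milder, probably favours the naive curve and cannot be sized from the document. The pooling is openly declared in section 3.2.1.

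The outputs are also secondary. The summary of changes labels them ad hoc, continuation is not an endpoint in section 1.4, and section 1.3 states no formal hypothesis.

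None of this removes the conflict. The third plot names the Safety Set, the rate names no population and so falls under a FAS default for tables, and a programmer who follows the definitions would produce the diluted result.

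**Conclusion.** The point holds as a mismatch between the populations named and the outputs planned. It does not establish that the analyses will be biased. On the literal sets, with time counted from the first index dose, the CS6 curve is near 100% to Month 12. The CS6 combined rate is then roughly 0.44-0.49 of the true rate with one year of open-label treatment and 0.56-0.64 with two. For CS16 the ratios are 0.61-0.65 and 0.71-0.78. These sizes rest on an assumed constant hazard and assumed annual dropout of 10-40%. On the full-arm reading the dilution is zero, and only the mixed make-up of the naive group remains. The SAP does not choose between the readings. The correction is worth making because it is cheap and readers will take the curves and rate at face value, but the outputs are descriptive.

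**What to change.** In section 3.2.4:

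1. State that the CS6 curve and all index-period discontinuation counts and rates use every patient dosed with volanesorsen in CS6 or CS16, whether or not they rolled over. Say that this overrides the FAS and Safety Set for these outputs. Set time zero at the first volanesorsen dose, define the event and censoring rule, and say which treatment start date enters patient-years.
2. Where only CS7 patients are used, start rollovers' time at risk at open-label Day 1 and leave index time out of the denominator.
3. As a supportive display, show CS7-New and index-placebo rollovers separately beside the combined naive curve.

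The cost is SAP wording and programming on index-study data. In a study of up to about 70 patients the split curves will be imprecise, which is why item 3 is only supportive. The reported rate may be less favourable than under the literal sets.

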3.3 Efficacy Analysis

Efficacy endpoints include: percent change and change in fasting lipid measurements, frequency and severity of patient reported abdominal pain, change from baseline in QOL, adjudicated acute pancreatitis events rate and frequency of other symptoms.

Efficacy analyses will be conducted in the FAS by the group presented in [Section 3.2.1](#).

For fasting lipid measurements and QOL (EQ-5D, SF-36), both the **Index Study Baseline** and the **Open-label Study Baseline** will be used. In the summary tables using the **Open-label Study Baseline**, visits are mapped to analysis visits as shown in [Section 3.2.1](#) for fasting lipid measurements and QOL (EQ-5D, SF-36) in the open-label study. In the summary tables using the **Index Study Baseline**, visits include the index study baseline visit, and the open-label study mapped post baseline visits.

Efficacy analyses for the fasting TG will be performed on FAS.

By patient listings will have all efficacy endpoints results collected in the open-label study.

Summary table and by patient listing will be generated by visit window, dose level, fasting TG and corresponding change from baseline value, nadir platelet, any pre-treatment adjudicated pancreatitis events, and abdominal pain event (average of intensity and yearly rate of frequency of moderate or severe events). Below visit windows will be utilized:

Visit Window	Dose Level	TG	Platelet Nadir	Abdominal Pain
0-3 months	week 1-13	month 3	day 1-91	week 2-14
3-6 months	week 14-26	month 6	day 92-182	week 15-27
6-9 months	week 27-39	week 38	day 183-273	week 28-40
9-12 months	week 40-52	month 12	day 274-364	week 41-53
12-15 months	week 53-65	week 64	day 365-455	week 54-66
15-18 months	week 66-78	week 76	day 456-546	week 67-79
18-21 months	week 79-91	week 90	day 547-637	week 80-92
21-24 months	week 92-104	week 104	day 638-728	week 93-105
24-27 months	week 105-117	week 117	day 729-819	week 106-118

3.3.2 Percent change and absolute change from baseline in fasting TG

The Month 3 analysis time point is at the end of Month 3 where the value is defined as the average of Week 12 (Day 78) and Week 13 (Day 85) fasting assessments. If one visit is missing, then the other visit will be used as the 3-month endpoint. If both visits are missing, then the 3-month endpoint will be set as missing.

The Month 6 analysis time point is at the end of Month 6 where the value is defined as the average of Week 25 (Day 169) and Week 26 (Day 176) fasting assessments. If one visit is missing, then the other visit will be used as the 6-month endpoint. If both visits are missing, then the 6-month endpoint will be set as missing.

The Month 12 analysis time point is at the end of Month 12 where the value defined as the average of Week 50 (Day 344) and Week 52 (Day 358) fasting assessments. If one visit is missing, then the other visit will be used as the 12-month endpoint. If both visits are missing, then the 12-month endpoint will be set as missing.

Percent change and absolute change from the **Open-label Study Baseline** at Month 3, Month 6, and Month 12 in this open label study, and percent change and absolute change from the **Index Study Baseline** in fasting TG at index study Month 3, Month 6, and Month 12, and the open label study Month 3, Month 6, and Month 12 will be summarized. For patients enrolled to extended treatment period, percent change and absolute change from the **Open-label Study Baseline** and percent change and absolute change from the **Index Study Baseline** in fasting TG at Week 64, 76, 90, and 104 will also be summarized.

These analyses will be repeated using on-treatment period data, which is defined as the last dose date of study medication + 28 days.

A descriptive summary of TG over time will be conducted overall and by age group (<65 years vs. ≥ 65 years). A descriptive summary of TG over time during on-treatment period will also be conducted overall.

3.3.3 Treatment response rates

Treatment response rate, where patients with fasting plasma TG < 750 mg/dL or achieving fasting TG ≥ 40% reduction from baseline at Month 3, Month 6, and Month 12 will be summarized overall and by age group (<65 years vs. ≥65 years). Four response rates are defined as following:

- Response rate 1 is defined as the proportion of patients with fasting plasma TG < 750 mg/dL at Month 3, Month 6, or Month 12 in the subset of patients with the **Open-label Study Baseline** fasting plasma TG ≥ 750 mg/dL.
- Response rate 2 is defined as the proportion of patients with fasting plasma TG < 750 mg/dL at Month 3, Month 6, or Month 12 in the subset of patients with the **Index Study Baseline** fasting plasma TG ≥ 750 mg/dL.
- Response rate 3 is defined as the proportion of patients who achieve fasting TG ≥ 40% reduction from the **Open-label Study Baseline** at Month 3, Month 6, or Month 12 for all patients with both baseline and post baseline results.
- Response rate 4 is defined as the proportion of patients who achieve fasting TG ≥ 40% reduction from the **Index Study Baseline** at Month 3, Month 6, or Month 12 for all patients with both baseline and post baseline results.

Response analysis will also be conducted using a range of fasting plasma TG thresholds for determination of responder status.

- Response rate 1 and 2 will also be conducted by using other response thresholds (e.g., 500, 880, 1000 mg/dL).
- Response rate 3 and 4 will also be conducted by using other response thresholds (e.g., ≥ 20%, 30%, 50%, 60%, 70% reduction).

Patients with both baseline and post baseline results will be included in the summary and counted in the denominators. Missing baseline or post baseline results will be excluded from the summary.

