1.1 Study Overview

This is an open-label study of:

Group 1: ISIS 304801-CS6 (index study) roll over FCS patients

Group 2: ISIS 304801-CS16 (index study) roll over FCS patients

Group 3: FCS patients who did not participate in the ISIS 304801-CS6 or ISIS 304801-CS16 index studies.

Up to approximately 70 patients will receive 300 mg once weekly volanesorsen for 52 weeks in the CS7 study.

Following the Week 52 visit, patients will have the option of participating in an expanded access program or continuing dosing for up to an additional 52 weeks until an expanded access program is approved and available in their country. Patients not participating in an expanded access program will enter a 13-week post-treatment evaluation period.

There is no primary efficacy endpoint. Both efficacy endpoints and safety endpoints will be summarized to evaluate the safety and efficacy of extended dosing with volanesorsen sodium 300 mg in patients with FCS.

Groups 1 and 2 (Qualification): During the qualification period, the eligibility of the patient to enroll in the open-label study will be determined. Final assessments from the ISIS 304801-CS6 or ISIS 304801-CS16 studies may be used for qualification. A period of up to 2 weeks after completion of the ISIS 304801-CS6 or ISIS 304801-CS16 index studies (unless approved by the Sponsor) is given to complete qualification. Qualified patients will retain the unique patient identification number that was assigned to them during the ISIS 304801-CS6 or ISIS 304801-CS16 index studies.

Group 3 (Screening and Qualification): At the time of consent, the patient will be considered enrolled into the study and will be assigned a unique screening number before any study procedures, including screening procedures, are performed.

Patients will be enrolled into the treatment phase of the study after all Screening (Group 3) and qualification assessments have been completed and after the Investigator has verified that they are eligible per criteria in protocol Sections 5.1 and 5.2. No patient may begin treatment prior to enrollment.

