Any patient who discontinues early from the Treatment Period should be followed as per the platelet monitoring rules shown in Section 8.6.3 of the protocol for the first 6 weeks after discontinuing Study Drug. Following this period, if the platelet count is stable (at least 3 consecutive values that are stable as determined by the Sponsor Medical Monitor and $> 100,000/\text{mm}^3$), the next platelet count should be taken within at least 6 weeks so that patients are monitored for at least 12 weeks after discontinuing Study Drug. Patients should also be strongly encouraged to attend applicable landmark visits at Weeks 12, 13, 25, 26, and 50, 52 (calculated based on the time elapsed since Day 1) to collect fasting lipid panels and conduct safety assessments in accordance with the Schedule of Procedures. Any patient who discontinues treatment after Week 44 should also be strongly encouraged to attend a final follow-up visit (Week 65 visit assessments) approximately 13 weeks after their last dose of Study Drug, in addition to the applicable landmark visits.

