3.2 General Overview of Analyses

3.2.1 *Statistical Methods*

All eCRF data, lab data transfers, as well as any outcomes derived from the data, will be provided in the patient data listings. Patient data listings will be presented for all patients enrolled into the study. Descriptive summary statistics including n, mean, median, standard deviation, standard error, interquartile range (25th percentile, 75th percentile), and range (minimum, maximum) for continuous variables, and counts and percentages for categorical variables.

Efficacy data including fasting lipid measurements, abdominal pain and QOL results will be mapped to analysis visit specified in the table below.

The intent of these visit windows is not to align with those prescribed for visit scheduling in the clinical study protocol but, rather, based on the protocol-defined target study day, to delineate mutually exclusive windows so that all efficacy assessments proximal to a particular study week can

be integrated to best represent the patient's status during that period of the study. If a patient discontinued early from the treatment period but attended applicable landmark visits at Weeks 12, 13, 25 and etc. to collect efficacy assessments, then those assessments collected at Early Termination visit and during post-treatment follow-up period should be mapped to analysis visits as well. If there are multiple assessments within a visit window, only scheduled visit will be used. If there are multiple scheduled assessments, for fasting lipid measurements and numeric QOL results, average will be used; for abdominal pain and character QOL results, the worst will be used. If the assessments are all unscheduled, the visit nearest the scheduled date will be used unless two visits are equally near, in which case the average will be used. For fasting lipid data, local lab data will not be used unless central lab assessments are not available at certain visit. When calculating the baseline and analysis endpoints, only if the data from central lab is missing, then the local lab data will be utilized.

Efficacy/PD measure	Mapped Visit (Week)	Target	Study Day Window
Fasting Lipid Assessment	Screening	-56 to -15	≤ -15
	Qual Visit	-14 to -7	-14 to <1
	1	1	1
	4	22	2 to 36
	8	50	37 to 64
	12	78	65 to 82
	13	85	83 to 106
	25	169	107 to 173
	26	176	174 to 197
	38	260	198 to 302
	50	344	303 to 351
	52	358	352 to 400
	extended treatment period		
	64	442	401 to 484
	76	526	485 to 575
	90	624	576 to 673

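### The four TG response rates leave out patients with no TG at the time point; a missing-as-non-response row and missing counts should stand beside them

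*SAP*

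**What the plan says.** SAP section 3.3.3 defines four response rates at Months 3, 6 and 12. Rates 1 and 2 are the share below 750 mg/dL among patients whose Open-label (rate 1) or Index Study (rate 2) baseline TG was at least 750 mg/dL. Rates 3 and 4 are the share with a reduction of at least 40% from those two baselines. The definitions of rates 3 and 4 already require a post-baseline result; those of rates 1 and 2 do not. The closing paragraph then applies one rule to all four: "Patients with both baseline and post baseline results will be included in the summary and counted in the denominators", and "Missing baseline or post baseline results will be excluded from the summary".

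Other sections decide who has a result:

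- Section 3.1: "Missing data will not be imputed".
- Section 3.3.2: each time point averages two visits and one is enough. For Month 12, "If both visits are missing, then the 12-month endpoint will be set as missing".
- Section 3.2.1: if a patient stops early but attends landmark visits, "then those assessments collected at Early Termination visit and during post-treatment follow-up period should be mapped to analysis visits as well".
- Section 2.1.2, on patients who stop early: "Patients should also be strongly encouraged to attend applicable landmark visits at Weeks 12, 13, 25, 26, and 50, 52".

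Efficacy is analysed in the Full Analysis Set (FAS), of which section 3.2.2 says: "The FAS represents the practically-feasible intent-to-treat (ITT) population as delineated in ICH Guideline E9". No other denominator and no missing-data sensitivity analysis is planned for the response rates.

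**The concern.** A patient with no TG at a time point is neither a responder nor a non-responder; the patient is not counted. If those who stop treatment are also those who do not come back for lipids, the rate describes the patients who stayed and were measured, not all those who started. Dependence on voluntary return grows with time. A TG taken at early termination fills only the window it falls in, so a patient who leaves before day 303 has a Month 12 value only by returning.

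No test depends on this. Section 1.3 states that there is no formal hypothesis, and section 1.1 that there is no primary efficacy endpoint. But where results are descriptive, the printed percentage is the result. Section 3.1.3 foresees interim analyses in support of regulatory filing. The rates are also split by group and by age, so denominators are small and each uncounted patient moves the rate more.

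**Working it through.** **No plan figure to reproduce.** The SAP gives no expected response rate, dropout rate or missing rate, and no sample size calculation.

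**Step 1: who drops out.** From the lipid window table in section 3.2.1 and the pairing rule in section 3.3.2:

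| Time point | Paired windows (study days) | Not counted if no TG in |
|---|---|---|
| Month 3 | 65–82 and 83–106 | days 65–106 |
| Month 6 | 107–173 and 174–197 | days 107–197 |
| Month 12 | 303–351 and 352–400 | days 303–400 |

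Stopping treatment does not by itself remove a patient. Only having no TG anywhere in the span does.

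**Step 2: formula.** Let N be the patients eligible for a rate, m those with no TG at the time point, and r the observed responders.

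- Planned rate: r/(N − m)
- Missing counted as non-response: r/N
- Missing counted as response: (r + m)/N
- Planned rate ÷ missing-as-non-response rate: N/(N − m) = 1/(1 − m/N)

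The factor is 1/0.9 = 1.11 at 10% missing, 1/0.8 = 1.25 at 20%, 1/0.7 = 1.43 at 30% and 1/0.6 = 1.67 at 40%. It is exact when both rates are computed on the same eligible patients.

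**Step 3: illustration.** N = 70 is the planned maximum from section 1.1 ("Up to approximately 70 patients will receive 300 mg once weekly volanesorsen for 52 weeks in the CS7 study"). The observed rate of about 50% and the missing shares are assumptions.

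| Missing | Planned rule | Missing = non-response | Missing = response |
|---|---|---|---|
| 7 (10%) | 32/63 = 50.8% | 32/70 = 45.7% | 39/70 = 55.7% |
| 14 (20%) | 28/56 = 50.0% | 28/70 = 40.0% | 42/70 = 60.0% |
| 21 (30%) | 24/49 = 49.0% | 24/70 = 34.3% | 45/70 = 64.3% |
| 28 (40%) | 21/42 = 50.0% | 21/70 = 30.0% | 49/70 = 70.0% |

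Over assumed observed rates of 40% to 70% and missing shares of 10% to 40%, the gap between the planned rule and missing-as-non-response runs from 4.0 points (25/63 against 25/70) to 27.6 points (29/42 against 29/70).

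**Step 4: effect of discontinuers who return.** Assume 70 patients, 21 of whom discontinue, with expected response of 60% on treatment and 10% off. The rate over all 70, whatever their treatment status, is (49 × 0.6 + 21 × 0.1)/70 = 31.5/70 = 45.0%. If a share k of the 21 has a TG in the window, the planned rule gives (29.4 + 2.1k)/(49 + 21k), and missing-as-non-response gives (29.4 + 2.1k)/70:

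| k | Planned rule | Missing = non-response |
|---|---|---|
| 0 | 60.0% | 42.0% |
| 0.25 | 55.2% | 42.75% |
| 0.50 | 51.2% | 43.5% |
| 0.75 | 47.8% | 44.25% |
| 1 | 45.0% | 45.0% |

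In this example the planned rule is too high unless every discontinuer is measured, and missing-as-non-response is slightly too low. The two rows bracket the full rate.

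**The case against.** The strongest reply is that this is an openly stated observed-case summary in a descriptive extension study. Response rates are not among the efficacy endpoints listed in section 1.4.1. Section 3.2.4 already shows disposition, discontinuation by month and Kaplan-Meier plots of treatment continuation, so a reader can see attrition. Counting missing as non-response is itself an assumption, and the factor in Step 2 measures that assumption rather than a proven bias. All of this stands and limits the weight of the point. It does not remove it: disposition tables show who stopped treatment, not who had no TG at Month 12.

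Four stronger readings are tempting and are not supported:

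- **Every early discontinuer drops out.** No. Those with a TG mapped to either window stay in, with off-treatment values that may lower the rate.
- **The rate is certainly inflated, by a known amount.** No. The direction depends on who is missing, and the SAP gives no share from which to compute the size.
- **All four rates have up to 70 patients.** No. Rates 1 and 2 are limited by baseline TG, and rates 2 and 4 need an Index Study Baseline, which Group 3 lacks.
- **The rule contradicts the intent-to-treat label.** Not strictly. That sentence describes who belongs to the FAS, and handling of missing values is a separate choice. The observed-case rate should nevertheless not be presented as an intent-to-treat result.

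One practical objection also holds. At an interim cut, some patients will not yet have reached Month 6 or 12, and counting them as non-responders would be wrong. The added row must exclude them.

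**Conclusion.** The point holds in a limited form. All four rates are calculated only among patients with a TG at both ends, and nothing in the plan shows what happens to them when the uncounted patients are included. The planned rate can never be lower than the missing-as-non-response rate on the same patients. Whether it is above the rate that complete follow-up would have given depends on missing TG going with stopping treatment, which is likely but not established. The dependence on return visits is greatest at Month 12.

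Separately, the definitions of rates 1 and 2 carry no post-baseline requirement while the closing paragraph of section 3.3.3 imposes one, so the section gives two denominators for them. The change should be made. It does not threaten any test, because none is planned.

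**What to change.** 1. Keep the observed-case row and label it as such.
2. For each rate and time point, add a row whose denominator is all FAS patients with the required baseline (rates 1 and 2: baseline TG of at least 750 mg/dL; rates 2 and 4: an Index Study Baseline) who have reached the end of the time-point window by the data cutoff (day 106, 197 or 400) or have discontinued the study. Count missing as non-response and label the row a conservative lower bound.
3. Show the number with missing TG for each rate and time point. At interim cuts, show patients who have not yet reached the time point separately, and give the observed-case row on the same patients so that the two rows differ only through missing TG.
4. Reword the definitions of rates 1 and 2 or the closing paragraph of section 3.3.3 so that each row has one stated denominator.

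No new data are needed. The cost is one extra row per table, and added rates that are less favourable than the observed-case ones wherever TG is missing.
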